**Cuff Leak Test and Airway Obstruction in Mechanically Ventilated ICU Patients
(COMIC): A Pilot Trial**

NCT: Not applicable

Date of Document: Dec 7, 2017

Cuff Leak Test and Airway Obstruction in Mechanically Ventilated ICU Patients (COMIC): A Pilot Randomized Controlled Trial Protocol

ABSTRACT

Introduction: Endotracheal intubation and mechanical ventilation are lifesaving interventions that are commonly done in the intensive care unit (ICU). The act of intubating someone can cause laryngeal edema that, if extensive enough, can cause airway obstruction after a patient is extubated. To date, the only test that is available to predict this complication is the cuff leak test (CLT). However, its diagnostic accuracy is uncertain as there have been no randomized controlled trials (RCT) examining this. Herein, we report the protocol for the Cuff leak and airway Obstruction in Mechanically ventilated ICU patients (COMIC) Pilot Trial to determine the feasibility of conduction a powered RCT to examine the impact of CLT on postextubation stridor and reintubation. Subsequently, describing the diagnostic accuracy of this test.

Methods: This will be a multi-center centered, pragmatic, double blinded RCT. We will include mechanically ventilated patients in the ICU, who are deemed ready to be extubated. All patients will have a CLT done prior to extubation. The results of the CLT in the intervention arm will be communicated to the treating physician, and decision to extubate will be left to the treating team, while the results of the CLT for patients in the control arm will not be communicated to the treating physician, and the patient will be extubated, regardless of the result of the CLT.

Objective: Although we will examine all clinical outcomes relevant for the future COMIC RCT, the primary outcomes of the COMIC Pilot Trial will be feasibility outcomes including: consent rate, recruitment rate, and protocol adherence. Clinical outcomes will include postextubation stridor, reintubation, emergency surgical airway, ICU mortality, in hospital mortality, duration of mechanical ventilation, and ICU length of stay in days.

INTRODUCTION

Endotracheal intubation and mechanical ventilation are lifesaving interventions. However, as with acute interventions, can be associated with serious complications. One such complication is laryngeal edema (LE) that occurs in 4-55% of patients¹⁻⁵. LE is thought to be caused by marked polymorphonuclear infiltration to the traumatized upper airway postintubation⁶. The incidence of LE increases as the duration of intubation accrues, but it can occur as early as the first 24 hours of intubation⁵. LE can result in airway narrowing and increased airflow velocity. It is postulated that narrowing of the lumen by 50% or more may result in postextubation stridor and respiratory distress⁷. As a result, 3.5% (range 0-10.5%) of patients with LE will fail an extubation attempt and require reintubation⁵. For various reasons, reintubation has a significant morbidity and mortality⁸⁻¹³.

Identifying patients with LE can be challenging, the presence of the endotracheal tube (ETT) precludes direct visualization of the upper airway prior to extubation, therefore, clinicians cannot accurately predict airway obstruction before it occurs. A cuff-leak test (CLT) was first described in 1988 as a surrogate for direct visualization and a screening for airway edema prior to extubation¹⁴. This test involves deflating the balloon cuff on an ETT and observing if the patient is able to breathe around it. If air can pass around the ETT, it suggests that the airway is patent and clinicians may proceed with extubation¹⁴. A small leak or complete absence of one, would suggest an airway obstruction.

There are conflicting results on the utility and accuracy of a CLT. To date, two meta-analyses of observational studies examined the diagnostic accuracy of a CLT^{5,15}. One meta-analysis reports

that a failed CLT is insensitive but a specific predictor of LE (pooled sensitivity and specificity 0.56; 95% CI, 0.48-0.63 and 0.92; 95% CI, 0.90-0.93, respectively) and reintubation (pooled sensitivity and specificity for reintubation 0.63; 95% CI, 0.38-0.84 and 0.86; 95% CI, 0.81-0.90, respectively)¹⁵. While the second meta-analysis also states that the failed CLT was associated with postextubation LE, particularly in patients with > 5 days duration of intubation (odds ratio [OR]=2.09; 95% CI, 1.28-2.89), it was not associated with higher odds of reintubation (OR=0.94; 95% CI, 0.32-1.57)⁵.

Despite the lack of high quality studies, an absent cuff leak usually results in delayed extubation and exposure to corticosteroids to empirically treat airway edema. A recent meta-analysis of 11 parallel randomized controlled trials (RCTs) with a total of 2472 patients examined the effect of prophylactic corticosteroids prior to extubation on postextubation stridor and reintubation¹⁶. Prophylactic corticosteroids use reduced the risk of postextubation airway events when compared to placebo or no treatment (RR 0.43; 95% CI 0.29-0.66, P=0.002)¹⁶. A subgroup analysis demonstrates that this benefit is only significant in patients that are deemed “high risk” for LE. Prophylactically treating unspecified patients shows no reduction in postextubation events and exposes patients to high dose steroids¹⁶. Moreover, a false positive CLT can unnecessarily delay extubation, leading to a prolonged length of stay in the intensive care unit (ICU), barotraumas, and increased risk of ventilator associated pneumonias¹⁷, therefore, exposing patients unnecessarily to these undesirable outcomes. On the other hand, if a CLT is not performed, or if in case of a false negative test, some patients may fail the extubation attempt and require reintubation.

Recent clinical practice guidelines for using CLT reflect this uncertainty. The American Thoracic Society guidelines on liberation of mechanical ventilation issued a weak recommendation for performing CLT in mechanically ventilated adults who are at high risk for postextubation stridor (conditional recommendation, very low certainty)¹⁷. There is also significant clinical equipoise. A recent unpublished survey found that 42% (12/26) of Canadian intensive care unit (ICU) physicians either never or rarely request to know the results of a cuff leak test prior to extubating a patient that is at moderate risk of laryngeal edema while 23% will always or usually order the test. Therefore, a large RCT is necessary to investigate the diagnostic accuracy of the CLT and its impact on patients' outcomes. Herein, we report the protocol for the COMIC Pilot Trial to determine the feasibility of undertaking a powered RCT to examine the impact of CLT on postextubation stridor and reintubation. Subsequently, describing the diagnostic accuracy of this test.

METHODS

Design

The COMIC (Cuff leak and airway Obstruction in Mechanically ventilated ICU patients) pilot trial will be a multicenter, randomized, concealed, blinded, parallel-group, pragmatic pilot trial.

Population

Eligible patients will be mechanically ventilated adults (>18 years) who are admitted to the ICU and an order to extubate has been provided by the treating physician.

Exclusion criteria

The exclusion criteria are:

- 1) A palliative care, a one-way extubation, or a decision to withdraw advances life support order has been written.
- 2) Pregnancy.
- 3) Patients at high risk for LE: burn patients, smoke inhalation injuries (as defined as singed facial hair or nasal hair, carbonaceous secretions/sputum, and known to be in an enclosed fire), blunt or penetrating trauma involving the neck and airway, postoperative head and neck surgeries, and patients admitted with airway edema to the ICU (e.g; anaphylaxis)¹⁸⁻²⁰.
- 4) Patients with either a difficult or traumatic endotracheal intubation.
- 5) Patients receiving mechanical ventilation via tracheostomy.
- 6) Known preexisting tracheolaryngeal abnormalities such as: vocal cord paralysis, tracheolaryngeal neoplasm, tracehomalasia, tracheolaryngeal stenosis, or previous head and neck surgeries.
- 7) Patients receiving systemic corticosteroids of greater than 30 mg of PO prednisone or equivalent, within 4 days prior to the decision to extubate.
- 8) Patients who failed extubation attempt within the current ICU admission.
- 9) History of postextubation airway obstruction.
- 10) The ICU physician declined enrolling the patient.
- 11) Patient had a failed CLT in the previous 24 hours.

Eligible non-randomized patients

We will record all patients who were eligible but not randomized for any of the following reasons: 1) The patient or substitute decision maker (SDM) declined consent; 2) The ICU physician declined enrolling the patient; 3) Any other reason.

Ethics

We will apply and obtain research ethics board (REB) approval at the participating centres. As most patients will be incapable at the time of enrolment, the SDM will provide consent *a priori* whenever possible. If the patient is able to consent at the time of enrolment then we will get written consent from them. We will follow the 2-phase, 13-step informed consent process that we have used in prior international trials²¹.

If we are unable to locate the SDM for *a priori* consent, then patients may be enrolled using deferred consent until the SDM can be contacted as permitted by local REBs. The consent encounter will occur as soon as possible. If, when found, the SDM response could be permission to continue all trial proceedings, or decline further trial proceedings. In the latter situation, data collected will be used up to that point, unless the SDM requests otherwise. For the patient who has no identifiable family member, or power of attorney to provide consent, we propose to continue study protocols while we attempt (and the ICU team attempts) to locate a SDM and/or the patient recovers. In the event that such a patient subsequently recovers to the extent that an informed consent can be provided, we will ask the patient for their consent.

Deferred consent model is crucial to ensure the proper conduct of the COMIC Trial. To begin with, extubating patients is a daily routine in the ICU, and should not be delayed unless there is a valid reason to do so. Therefore, we will allow a one hour window for the study Research Coordinator (RC) to obtain *a priori* consent whenever possible, but mandating *a priori* consent

will make this study infeasible. Although CLT is commonly performed in the ICU prior to extubation, there is no clear evidence that this practice benefit patients⁵, in fact performing a CLT routinely could result in harm in some patients by delaying extubation unnecessarily and exposing them to high dose corticosteroids. The results of this trial will inform practice about an intervention that is being used for decades with lack of high quality evidence. We have successfully used deferred consent model in recent a RCT²². Several other large, multicenter, international RCTs have successfully used deferred consent model in acute settings²², and it would not have been possible to inform practice and conduct those trials without a deferred consent model.

Randomization and allocation concealment

The study RC will use the web-based system RANDOMIZE.NET (<http://www.randomize.net/>) to randomize eligible patients in a 1:1 allocation using undisclosed variable block sizes. Randomization will be stratified by: a) ETT size into three strata (6, 7, 8 mm ETTs), and b) duration of mechanical ventilation prior to randomization into two strata (>7 days and \leq 7days).

Intervention

The Respiratory Therapist (RT) will perform the CLT on all enrolled patients. The patients will first be switched to volume assist-control (V-AC) with a respiratory rate of 10 breaths/min (to allow patient assist), constant flow of 60 l/min, and tidal volume set to match the average tidal volume currently being delivered during supportive ventilation. The RT will document the average exhaled volume over 3-5 breaths after switching to V-AC. The test will be performed by deflating the ETT balloon cuff with a 10 cc syringe, and: a) auscultation with a stethoscope to identify audible air leak around the ETT, and b) measuring the difference between the average

exhaled volume prior to cuff deflation and the average exhaled volume over 3-5 breaths after cuff deflation.

We define a “failed CLT” as the RT being unable to identify air leak during auscultation.

Patients randomized to the intervention arm will have the results of the CLT (whether failed or passed CLT) communicated to the treating physician; the treating physician will decide whether to proceed with extubation or not based on the CLT results. It is at the discretion of the treating physician to provide corticosteroids (4-5 mg of intravenous dexamethasone every six hours for up to 24 hours, with the last dose given one hour preceding extubation) and/or delay extubation by 24 hours should the patient fail the CLT²³.

In the control arm of this trial; the treating physicians and healthcare workers will be blinded to the results of CLT; therefore, the RT will proceed with extubation without delay or administering systemic steroid, regardless to the CLT results.

Patients, physicians, RCs, study investigators, adjudicators, and data analysts will be blinded to the results of CLT in the control group.

OUTCOMES

Feasibility Outcomes

Although we will report all clinical outcomes relevant for the future COMIC RCT, the primary outcomes of the COMIC Pilot Trial will be the following feasibility outcomes:

- 1) Consent Rate: a successful consent rate will be defined as 70% of SDMs or patients approached to consent, choosing to participate in the trial. This will be calculated as the overall proportion of SDMs or patients consenting out of those approached (with 95% CI). As this is a Pilot Trial, the consent rate will be reviewed monthly and if applicable, barriers to informed

consent will be discussed and factors associated with improved consent as produced by the CCCTG Research Coordinators will be employed²¹.

2) Recruitment Rate: a successful recruitment rate will be defined as achieving enrolment of 40 patients, conventionally expressed as four patients per month over the duration of the trial. While the pilot trial is ongoing, recruitment will be reviewed weekly and the screening records will be reviewed monthly with the cases of missed eligible patients reviewed. If applicable, barriers to enrolment will be addressed to maximize recruitment. The recruitment metric will be measured and interpreted at the end of the pilot trial by calculating the mean number of recruited patients per active screening month.

3) Protocol Adherence: Successful adherence will be defined as $\geq 80\%$ of patients assigned to the intervention arm being treated as previously described. The adherence will be calculated as the proportion of patients that were assigned to the control arm being extubated after CLT being performed and the portion of people that assigned to the intervention arm who are given the prescribed steroids for a failed CLT. As this pilot trial is ongoing, we will review adherence monthly and investigate the reasons for compliance failure. All reasons for either failure to extubate after a failed CLT in the control arm will be investigated. The RC will review the Respiratory Therapists' notes, and the medication profile to determine actual compliance. All reasons for non-compliance will be recorded for both groups using distinguishing clinical reasons (eg. Palliation, death, consent withdrawal, errors).

Clinical Outcomes

The clinical outcomes are:

- 1) Postextubation stridor: defined as an audible high pitched inspiratory noise caused by turbulent airflow through the narrowed airway that is detectable with or without a stethoscope within 48 hours of extubation.
- 2) Clinically significant postextubation stridor: Defined as stridor (see definition above) that requires medical intervention such as the administration of systemic steroids, racemic epinephrine, or Heli-ox.
- 3) Reintubation: defined as reintubation within 72 hours of original extubation while in the ICU. Reasons for intubation will be recorded.
- 4) Emergency surgical airway: defined as performing urgent tracheostomy or cricothyroidotomy for a life-threatening airway obstruction.
- 5) In ICU mortality.
- 6) In hospital mortality truncated at 30 days.
- 7) Duration of mechanical ventilation: defined as time on the ventilator after randomization in days.
- 8) ICU length of stay in days.

Clinical outcome adjudication

The RC will enter data in a web-base and send relevant clinical information to staff at the methods centre who will validate data and prepare adjudication packages for all clinical outcomes. Two independent blinded physicians will adjudicate post extubation stridor and reintubation outcomes.

Data collection and follow-up

The RC will screen the ICU Monday to Friday to avoid incurring additional weekend on-call costs. RC will collect information including the patient baseline data (e.g., demographics, illness severity, advanced life support including duration of mechanical ventilation, daily data (e.g., CLT results, postextubation stridor, rate of reintubation, steroids administered), and source documentation that will help with adjudication of outcomes. RC will review patients daily in the ICU where the trial data including mortality, length of stay, and length of mechanical ventilation will be gathered. Once patients are discharged from the ICU they will no longer be followed daily, but incidence of in hospital mortality will be assessed at time of hospital discharge. Mortality, duration of ventilation, and ICU stay outcomes will be censored at 60 days.

Duration of the COMIC Pilot Trial

We anticipate that 10 months will be required to recruit 40 patients. A subsequent three months will be needed to validate the data, adjudicate the outcomes, analyze, interpret and present results. The total duration of the Pilot Trial may take up to 13 months to complete.

Analysis of the COMIC Pilot Trial

Calculation of consent and recruitment feasibility outcomes for the COMIC Pilot Trial will not require analysis by group, however compliance rates will have to be assessed for each group. Therefore, clinical outcomes will be analyzed as means or proportions in each arm. In addition, given the small sample size and short duration, we will not conduct any subgroup or interim analyses. An independent data safety and monitoring board will be created for the large COMIC RCT.

The proportion of patient in the two groups with the primary and secondary outcomes will be

analyzed using the Mantel-Haenszel χ^2 test or Fisher exact test. A t-test will be used for continuous outcomes and a statistical significance will be set at alpha=0.05. We will develop a full statistical analysis plan adherent to the intention to treat principle and some subgroup analysis (e.g., size of endotracheal tube).

DISCUSSION

Extubation can be a precarious step for patients admitted to the ICU. Therefore, critical care physicians undertake the utmost cautions prior to extubating patients. Moderate quality evidence supports the use of a spontaneous breathing trials with inspiration pressure augmentation as a method to predict a patient's capacity to breath upon liberation from the ventilator²⁰. CLT is the most commonly used test to detect LE in mechanically ventilated patients. However, the diagnostic accuracy and impact on clinical outcomes in average risk patients are unclear. Therefore, recent guidelines issued a weak recommendation to perform CLT prior to extubating high risk patients (i.e. traumatic intubation, a large endotracheal tube, or reintubated after an unplanned extubation)¹⁷. Patients who fail a CLT are often treated with high dose systemic corticosteroids and extubation may be delayed, both outcomes are likely not desirable by most patients.

To our knowledge, only observational studies showed that in subsets of patients; a CLT may help identify patients at higher risk of airway obstruction. We therefore, have presented a protocol for a pilot RCT to determine the feasibility of examining the effect of using CLT on postextubation complications, versus not using the test. Physician and public acceptance of performing such a

protocol is uncertain and it is integral that the recruitment rate, consent rate, and adherence rate are examined before a large scale RCT is pursued.

In conclusion, this protocol describe in detail the design and methodology of COMIC Pilot Trial. We believe that the results of this trial will help inform the design and the conduct of a large RCT examining the effect of bedside CLT on postextubation events in average risk mechanically ventilated patients.

References

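### Does listing physician refusal both as an exclusion and as a reason eligible patients were not randomised leave the pilot's results ambiguous?

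*Protocol*

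**What the plan says.** In the Methods, the last but one of the eleven exclusion criteria is "10) The ICU physician declined enrolling the patient". The section that follows, Eligible non-randomized patients, opens with "We will record all patients who were eligible but not randomized for any of the following reasons". After refusal of consent, it gives the remaining reasons as "2) The ICU physician declined enrolling the patient; 3) Any other reason".

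Under Feasibility Outcomes, the consent rate is the "overall proportion of SDMs or patients consenting out of those approached (with 95% CI". The recruitment metric is obtained by "calculating the mean number of recruited patients per active screening month". Adherence is a proportion of patients assigned to an arm. During the trial, "the screening records will be reviewed monthly with the cases of missed eligible patients reviewed".

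The Discussion gives the motive for the pilot: "Physician and public acceptance of performing such a" "protocol is uncertain and it is integral that the recruitment rate, consent rate, and adherence rate" be examined before a large trial is undertaken.

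**The concern.** One event carries two incompatible labels. As an exclusion, a physician's refusal takes the patient out of the eligible group. As a reason for non-randomisation, it leaves the patient in that group. Two sites could file the same refusal differently, and the pooled number eligible would then have no single meaning.

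This seems to matter more here than in most trials, because the Discussion names physician acceptance as an open question. None of the three feasibility rates separates a physician's refusal from other causes of slow enrolment, so the screening log is where one would look for it. If its denominator is unclear, the pilot might meet its thresholds and still not show how often physicians held patients back. The natural remedy would be to delete the exclusion criterion and to report refusals, and randomised patients, as proportions of those eligible.

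**Working it through.** **Step 1. The two listings side by side.** The wording of the event is identical. The exclusion list says who does not enter the trial. The next section says what is to be recorded about patients who did not enter. Only the second is a recording instruction, and it names physician refusal. A workable reading is therefore that the criterion is the enrolment gate and the following section is the logging rule. The protocol does not state this reading, but it is the one under which both lines have a purpose. If the criterion also governed logging, reason 2 could never apply to anyone.

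**Step 2. Which planned results use the number eligible?**

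| Primary feasibility outcome | Success threshold | Denominator | Uses number eligible? |
|---|---|---|---|
| Consent rate | 70% | patients or substitute decision makers approached | no |
| Recruitment rate | 40 patients, four per month | active screening months | no |
| Adherence | at least 80% | patients assigned | no |

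The recruitment target agrees with the planned duration: 4 per month × 10 months = 40. It does not depend on how a refusal is labelled. The clinical outcomes compare randomised groups and do not involve the screening log.

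**Step 3. What would differ between the readings?** The protocol gives no refusal count, so these inputs are assumptions: 40 randomised, 10 consent refusals, no other losses, and 5, 10 or 20 physician refusals.

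- Refusals treated as exclusions: eligible = 40 + 10 = 50, and randomised/eligible = 40/50 = 80.0%.
- Refusals treated as eligible: eligible = 50 + physician refusals.

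| Physician refusals | Eligible | Randomised/eligible | Refusals/eligible | Consent rate |
|---|---|---|---|---|
| 5 | 55 | 40/55 = 72.7% | 5/55 = 9.1% | 40/50 = 80.0% |
| 10 | 60 | 40/60 = 66.7% | 10/60 = 16.7% | 40/50 = 80.0% |
| 20 | 70 | 40/70 = 57.1% | 20/70 = 28.6% | 40/50 = 80.0% |

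The two eligible counts differ by exactly the number of physician refusals. Once that number is recorded, either count follows from the other by addition or subtraction. The two ratios that move are not defined anywhere in the protocol.

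**Step 4. Can the size of the effect be estimated?** No. If refusal is an assumed share r of patients meeting the clinical criteria and nothing else is lost, eligible = 40/(1 − r). A count that leaves refusals out is then too low by (eligible − 40)/eligible = r. The undercount is the assumption returned unchanged and says nothing about how large the problem would be.

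**The case for a change.** The strongest argument is that the promise to record reasons covers only patients who were eligible, and the protocol makes no matching promise to log excluded patients by criterion. A site that applied the exclusion literally could leave a refusal outside the record, and no later analysis plan could recover an event that was never logged. Refusal is also plausible: the Introduction reports that 23% of surveyed physicians always or usually order the test, while the control arm withholds its result.

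Part of this stands. The wording is untidy, and sites could differ. But information is lost only if a site disregards a reason that the protocol spells out, which is a departure from the plan rather than a result of following it.

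The link to the monthly review is also weaker than it looks. The protocol does not say whether a missed eligible patient includes a known refusal or only someone never identified or approached.

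The Discussion names the three rates by which acceptance is to be judged, and refusals already lower one of them, patients recruited per month. Wanting physician refusal shown as its own proportion is a reasonable reporting preference, but the wish would be the same if the exclusion criterion did not exist.

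Deleting the criterion is not free either. It is the only eligibility rule that gives effect to a physician's refusal; the second listing merely records it.

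**Conclusion.** The inconsistency is real but confined to a label in the screening log. The effect on the three primary feasibility outcomes, their thresholds and the clinical comparisons is nil. The only quantity that moves is the number eligible, and it moves by exactly the number of physician refusals, which the protocol already asks sites to record.

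This conclusion rests on sites recording refusals under the reason provided. It also rests on the outcome definitions in the protocol, since the statistical analysis plan is not at hand. Whoever draws up the screening form can file such patients as eligible but not randomised, provided they meet all other criteria, and show the number in the flow diagram. Amending the plan would tidy the wording without changing any result it sets out to produce.

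### Research coordinators are listed as blinded to control-arm cuff leak results that they are also told to collect, and the abstract's double-blind label does not fit the design

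*Protocol*

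**What the plan says.** The Intervention section names six roles as masked, and says what they are masked to: "Patients, physicians, RCs, study investigators, adjudicators, and data analysts will be blinded to the results of CLT in the control group". The same section gives the scope of testing: "The Respiratory Therapist (RT) will perform the CLT on all enrolled patients".

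Under Data collection and follow-up, the RC's task list includes "daily data (e.g., CLT results, postextubation stridor, rate of reintubation, steroids administered". No arm is excluded.

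Under Feasibility Outcomes, item 3 (Protocol Adherence), the RC has a further task: "The RC will review the Respiratory Therapists' notes, and the medication profile to determine actual compliance". That item adds "All reasons for non-compliance will be recorded for both groups using distinguishing clinical reasons", and also "All reasons for either failure to extubate after a failed CLT in the control arm will be investigated". The analysis section says "compliance rates will have to be assessed for each group".

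On the label, the Abstract says "This will be a multi-center centered, pragmatic, double blinded RCT", while Methods, Design says only that the trial is blinded. The Abstract and the Intervention section both provide that the treating physician is told the result in the intervention arm and not in the control arm. The Intervention section makes clear that in the intervention arm both passes and failures are reported.

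**The concern.** There are two problems of the same kind: the protocol claims masking that its own procedures do not deliver.

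The first concerns the RC. A person cannot be masked to control-arm CLT results and also collect CLT results for all patients. This matters because the RC gathers postextubation stridor data in the same list and sends the methods centre the clinical information from which adjudication packages are built. Stridor is defined by a sound heard with or without a stethoscope, so it is the kind of outcome for which knowledge of a failed test is worth keeping away from those who gather the data.

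The second concerns the label. A reader normally takes double blinding to mean that the treating side does not know the allocation. Here it does, and the design depends on it, since the physician acts on the result in one arm. The pilot is meant to inform a larger trial, so an unclear masking scheme would be carried forward.

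**Working it through.** The plan gives no figure to reproduce. The check sets the passages side by side and counts who is affected.

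**Step 1. Is the RC's masking compatible with the RC's tasks?**
- Intervention: the RC is masked to control-arm CLT results.
- Intervention: the test is done on all enrolled patients, so a result exists for every control patient.
- Data collection and follow-up: the RC collects CLT results, with no limit to one arm.
- No sealed form, restricted field or separate unmasked person is described anywhere for control-arm results.

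Taken literally, the second, third and fourth statements put control-arm results in the RC's hands, which the first statement denies.

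**Step 2. How many patients?** Inputs: 40 patients (Feasibility Outcomes, item 2, and Duration of the COMIC Pilot Trial) and 1:1 allocation (Randomization and allocation concealment).
- Control patients: 40 × 1/2 = 20. With stratification and variable blocks the split may not be exact, hence about 20.
- Share of the trial: 20/40 = 50%.
- Roles in the list: patients, physicians, RCs, study investigators, adjudicators, data analysts = 6. The contradiction is shown for 1 of the 6.

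**Step 3. Do the adherence tasks add independent proof?**
- Therapists' notes: the therapist performs the test, so the notes could show the result, but the protocol does not say that they do.
- Compliance in both groups: control-arm adherence is defined as extubation after the test has been performed. That can be judged without knowing the result.
- Follow-up of control patients not extubated after a failed test: finding these patients does need the result. But the sentence is incomplete (an *either* with no *or*), and it names nobody as the person who investigates.

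These are possible further routes to the RC. None is established, and Step 1 does not need them.

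**Step 4. Does the double-blind label fit?**
- Intervention arm: the physician receives a result for each of about 20 patients, whether passed or failed.
- Control arm: the physician receives a result for none of about 20 patients.
- Receiving or not receiving a result therefore identifies the arm for about 20 + 20 = 40 of 40 patients.

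The list in the Intervention section remains accurate for physicians, because it claims only masking to control-arm results. It is the Abstract's label that overstates.

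**The case against.** The best defence on the RC is that the data-collection list is a general list of examples, while the blinding sentence is a specific rule. Read together, the rule could supply the missing arm limit, which would leave an unstated routing step and not an impossible instruction. That reading is possible, but the protocol does not state it and gives no other way for control-arm results to be captured. What stands of this defence is that 20 of 20 control patients is an upper bound resting on one listed item.

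On the label, the defence is that the Abstract itself goes on to describe disclosure in one arm only, so an attentive reader or ethics board is told the facts. This is fair and limits the harm. It does not make the label correct. Nor does the plain description as blinded under Design contradict the Abstract; it is only less specific.

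A reader might infer more than the documents support:
- *That the RC's review of the therapists' notes proves exposure.* The only written record the Intervention section expressly requires is the exhaled volume before cuff deflation; where the auscultation finding is recorded is not stated.
- *That the RC judges stridor at the bedside.* The protocol says the RC collects the data, not that the RC makes the assessment.
- *That adjudication is compromised.* Two independent physicians described as blinded adjudicate stridor and reintubation, and nothing shows that results or arm reach them.

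**Conclusion.** The point holds in two parts, both wrong as written.

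1. The claim that RCs are masked to control-arm CLT results conflicts with their data-collection task, for up to about 20 of 40 patients. This assumes that the CLT item in the RC's list means what it says and covers both arms.
2. The double-blind label is wrong: the treating physician can tell the arm for about 40 of 40 patients. This follows directly from the disclosure rule.

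The consequence is limited. The primary outcomes are feasibility measures, and consent and recruitment rates are not touched. Any effect would fall on secondary clinical outcomes, chiefly stridor. The protocol gives nothing from which a size of bias could be derived, and it would be a mistake to read this point as showing that the stridor comparison is biased. This should be corrected because the masking statement is inaccurate and the remedy is cheap.

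**What to change.** **Label.** Replace the double-blind wording in the Abstract, and align the Design section, with a statement by role. The treating physician and the respiratory therapist are not masked to allocation. The RC performs the randomization, and no masking of the RC to allocation is described. The roles listed under Intervention are masked to control-arm CLT results.

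**Routing.** Limit the CLT item in the RC's data list to the intervention arm. Have the therapist who performs the test enter control-arm results directly in a restricted form or database field. Keep that record closed to the RC and to those preparing adjudication packages until adjudication is complete. Methods-centre staff are a poor choice to hold these results, because they assemble the packages.

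**Compliance.** Complete the sentence on control patients not extubated after a failed test, and name who investigates. Any check that needs a control-arm result should use the restricted record and should not pass through the RC.

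**Alternative.** If this routing is not adopted, remove RCs from the blinded list. The text would then be true, but the person collecting stridor data would know the control-arm results.

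**Cost.** Wording changes in a few sections, one routing step for about 20 results, and a less favourable blinding label. Masking adjudicators or analysts to allocation in both arms would be a separate design decision; this point does not require it.
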